6. STUDY OBJECTIVES AND ENDPOINTS

Table 6: Study Objectives and Endpoints

Primary Objective	Primary Endpoint
The primary objective of the study is to evaluate the efficacy of BIIB104 in subjects with CIAS, using the Working Memory Domain of the MATRICS Consensus Cognitive Battery (MCCB).	The primary endpoint is the change from baseline in MCCB Working Memory Domain score to Week 12.
Secondary Objectives	Secondary Endpoints

To evaluate the safety and tolerability of BIIB104 in subjects with CIAS
 
To evaluate the efficacy of BIIB104 in subjects with CIAS on measures of cognition, functioning, and psychiatric symptomology, as measured by:
 
 • University of California, San Diego Performance Based Skills Assessment–Brief, international version (UPSA-Bi) • Schizophrenia Cognition Rating Scale (SCoRS) • MCCB • Structured Clinical Interview for Positive and Negative Syndrome Scale (SCI-PANSS) • Clinical Global Impression–Severity (CGI-S) and Clinical Global Impression–Improvement (CGI-I) 	
Incidence of adverse events (AEs) and serious adverse events (SAEs) reported during the study, Scale for the Assessment and Rating of Ataxia (SARA), Columbia Suicide Severity Rating Scale (C-SSRS)
 
Change from baseline in UPSA-Bi assessment to Week 12
 
Change from baseline in SCoRS assessment to Week 12
 
Change from baseline in MCCB Composite and Individual Domain scores (excluding Working Memory Domain) to Week 12
 
Change from baseline in SCI-PANSS total score and subscale scores to Week 12
 
Change from baseline in CGI-S to Week 12
 
CGI-I at Week 12

CONFIDENTIAL

The information contained herein may not be used, disclosed, or published without the written consent of Biogen MA Inc.

This clinical study collects samples that under separate optional consent may be used for future scientific and genetic research. Objectives related to this future research have not been determined.

CONFIDENTIAL

The information contained herein may not be used, disclosed, or published without the written consent of
Biogen MA Inc.

7. STUDY DESIGN

This is a Phase 2, randomized, double-blind, placebo-controlled, parallel-group study to evaluate the safety, tolerability, and efficacy of BIIB104 in subjects with CIAS. Approximately 219 male and female subjects with stable schizophrenia from age 18 to 55 years, inclusive, will be recruited. Dosing with BIIB104 0.15 mg BID and 0.5 mg BID versus placebo will be evaluated over a treatment phase of 12 weeks. The study will be conducted at approximately 80 sites globally.

The study includes a screening phase, a placebo lead-in phase, a randomized treatment phase, and a safety follow-up (SFU) phase to begin after the last dose of study treatment. The primary analysis will be conducted after 12 weeks of placebo-controlled treatment.

[figure not shown]
Screening evaluation will occur up to 35 days prior to randomization. Once eligibility has been established, a 7-day Placebo Lead-In evaluation will be conducted to assess the subject's ability to comply with dosing requirements; this evaluation must be completed no earlier than 3 days prior to the Baseline/Day 1 Visit. After Sponsor reconfirmation of eligibility and completion of baseline measurements at the Baseline/Day 1 Visit, subjects will be randomized in a 1:1:1 ratio to receive BIIB104 0.5 mg, BIIB104 0.15 mg, or placebo (planned for 73 subjects per treatment group). The randomization will be stratified by region. Subjects will be dosed at approximately 12-hour intervals for approximately 12 weeks. Total duration of subject participation will be approximately 19 weeks from screening to final follow-up visit.

See [Figure 1](#) for a schematic presentation of the study design.

CONFIDENTIAL

The information contained herein may not be used, disclosed, or published without the written consent of
Biogen MA Inc.

Figure 1: Study 263CS201 Schematic

N = number of subjects; MCCB = MATRICS Consensus Cognitive Battery; BID = twice daily.

*Note: The Placebo Lead-In evaluation may begin any time after eligibility has been established based on screening assessments, provided that the Placebo Lead-In is completed no earlier than 3 days prior to the Baseline/Day 1 Visit.

CONFIDENTIAL

The information contained herein may not be used, disclosed, or published without the written consent of Biogen MA Inc.

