10. DISCONTINUATION OF STUDY TREATMENT AND WITHDRAWAL OF SUBJECTS FROM THE STUDY

10.1. Discontinuation of Study Treatment

A subject must permanently discontinue study treatment for any of the following reasons:

- The subject becomes pregnant. Study treatment must be discontinued immediately, and the pregnancy must be reported according to the instructions in Section [15.4.1](#).
- Any seizure event. If a seizure event is suspected, the subject must discontinue study treatment and be referred to a neurologist for appropriate follow-up (see Section [7.3](#)). An effort should be made to collect a [REDACTED] as soon as possible after the event.
- The subject withdraws consent.
- The subject experiences a medical emergency that necessitates permanent discontinuation of study treatment or unblinding of the subject's treatment assignment.
- The subject experiences an AE requiring continued treatment that meets exclusionary criteria.
- The subject has confirmed ALT or AST $>5 \times$ ULN, or confirmed ALT or AST $>3 \times$ ULN and bilirubin $>2 \times$ ULN.
- Depending on the specifics of the subject's C-SSRS as assessed by the Investigator, subjects must have their suicidality managed appropriately by clinicians and must discontinue from the treatment.
- At the discretion of the Investigator, for medical reasons.
- At the discretion of the Investigator or the Sponsor, for noncompliance with the terms of the protocol.
- The primary reason for discontinuation of study treatment must be recorded in the subject's case report form (CRF).

All subjects who discontinue study treatment prematurely will be asked to remain in the study and continue all protocol-specified visits and procedures. At a minimum, these visits should include assessment of AEs/SAEs and concomitant medications and key clinical assessments. Subjects who discontinue study treatment prematurely will also be asked to return to the study site for an SFU Visit 14 days after receiving the last dose of study treatment.

CONFIDENTIAL

The information contained herein may not be used, disclosed, or published without the written consent of Biogen MA Inc.

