4.5.3.1 Quantitative Analyses

Hematology, serum chemistry, and urinalysis will be summarized by treatment group and visit. Descriptive statistics will be presented at each visit by treatment group, including number of subjects, mean, standard deviation, median, 25%, 75% quartiles, minimum, and maximum values.

Changes from baseline in quantitative laboratory values will be summarized using descriptive statistics by treatment group and visit. Plots of mean values by visits will be presented for numeric laboratory parameters, except for mean corpuscular volume (MCV), mean corpuscular hemoglobin (MCH), and mean corpuscular hemoglobin concentration (MCHC).

Individual subject listings of clinical laboratory parameters at each visit will be provided. Values for hematology, serum chemistry, and urinalysis values outside the central laboratory reference ranges will be flagged on the individual subject data listings.

Visit windows for by visit summaries

For laboratory by visit summaries, the analysis visit is defined by visit windows in the table below. If there is more than 1 value in the same analysis visit window for a certain parameter for a subject, then the closest record to the target visit day will be used for the by visit analysis. If there are 2 values in the same analysis visit window with the same distance from the target visit day for a certain parameter for a subject, then the record with the later date will be used for the by visit analysis. If there are 2 values on the same day for a certain parameter for a subject, then the record with the later time will be used for the by visit analysis.

Table 6: Visit Windows for Laboratory

Analysis visit	Target visit day	Analysis visit window
Baseline	1	Most recent non-missing pre-dose value
Week 1	8	[2, 10]
Week 2	15	[11, 21]
Week 4	29	[22, 42]
Week 8	57	[43, 70]
Week 12	85	[71, one day before start of safety follow-up]
Safety follow-up	Safety follow-up	[start of safety follow up, the end of study]

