4.5.7 SARA

Descriptive statistics will be used to summarize SARA measurements at each visit for each treatment group. Individual subject listings of SARA at each timepoint will also be provided by treatment group.

Table 11: Visit windows for SARA

Analysis visit	Target visit day	Analysis visit window
Baseline	1	Most recent non-missing pre-dose value
Week 1	8	[2, 10]
Week 2	15	[11, 28]
Week 6	43	[29, 63]
Week 12	85	[64, one day before start day of safety follow-up]
Safety follow-up	Safety follow-up	[Start day of safety follow-up, the end of study]

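### SAP Tables 6 and 11 push the Day 85 laboratory and SARA results of subjects who stop drug early but stay in the study out of the Week 12 row

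*Protocol*

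**What the plan says.** Protocol Section 7 describes "a safety follow-up (SFU) phase to begin after the last dose of study treatment", and SAP 2.1 repeats this. Protocol 10.1 adds two requests for early stoppers. First: "All subjects who discontinue study treatment prematurely will be asked to remain in the study and continue all protocol-specified visits and procedures". Second, they are also asked to "return to the study site for an SFU Visit 14 days after receiving the last dose of study treatment".

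The SAP then maps results to analysis visits:

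- Table 6 (laboratory, SAP 4.5.3.1): Week 12 is "71, one day before start of safety follow-up" and the follow-up row is "start of safety follow up, the end of study".
- Table 11 (SARA, SAP 4.5.7): Week 12 is "64, one day before start day of safety follow-up" and the follow-up row is "Start day of safety follow-up, the end of study".
- If a laboratory window holds several records, "then the closest record to the target visit day will be used for the by visit analysis". The target given for the follow-up row is a label, not a day number. SAP 4.5.7 has no selection rule for SARA.

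Neither table makes an exception for a subject who is off drug but still attending, and the SAP does not link the start of follow-up to a date variable.

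**The concern.** The two window definitions work only if follow-up comes after Week 12. That is true for a completer. For a subject who stops drug early and stays, Protocol 10.1 places follow-up among the scheduled visits, and the tables then exclude a Day 85 result from Week 12.

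SARA is part of a named secondary endpoint, and its only planned summary is descriptive statistics by visit, plus listings. If stopping differs between arms, the composition of the Week 12 SARA and laboratory rows would differ with it. The follow-up row, meant to show status about two weeks off drug, could also receive a value from much later.

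**Working it through.** No figure in the plan has to be reproduced here. The check applies the windows to nominal visit days.

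**Inputs**

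- L is the study day of last dose; the planned last dosing day is Day 85 (Protocol Table 4).
- The Week 12 visit is on Day 85, within ±3 days, so Days 82 to 88 (Protocol Table 4 and its footnote 2).
- S is the start of follow-up. Two readings are possible: the follow-up visit, S = L + 14 (Protocol 10.1), or the phase, which begins after the last dose, so S = L + 1 at the earliest (Protocol 7, SAP 2.1).
- Week 12 is [71, S − 1] for laboratory and [64, S − 1] for SARA. Follow-up is [S, end of study].

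**Results**

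| | S = L + 14 (visit) | S = L + 1 (phase) |
|---|---|---|
| Week 12 closes on | Day L + 13 | Day L |
| Day 85 result outside Week 12 | 85 > L + 13, so L ≤ 71 | 85 > L, so L ≤ 84 |
| Same, visit held on Day 82 | L ≤ 68 | L ≤ 81 |
| Same, visit held on Day 88 | L ≤ 74 | every L up to the planned Day 85 |
| Laboratory Week 12 window void | L + 13 < 71, so L ≤ 57 | L < 71, so L ≤ 70 |
| SARA Week 12 window void | L + 13 < 64, so L ≤ 50 | L < 64, so L ≤ 63 |

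Between the void cutoff and the Day 85 cutoff, the window exists but no scheduled laboratory or SARA assessment falls in it at nominal days.

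**Control.** For a completer with L = 85, S is Day 99 or Day 86, and Day 85 is in Week 12 under both readings. At nominal days, the fault concerns only those who stop before Day 85.

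**Example, L = 20, follow-up visit on Day 34**

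- Visit reading, laboratory: Week 12 becomes [71, 33], which is void. Day 34 fits Week 4 [22, 42] and follow-up. Day 57 fits Week 8 [43, 70] and follow-up. Day 85 fits follow-up only.
- Visit reading, SARA: Day 43 fits Week 6 [29, 63] and follow-up. Day 85 fits follow-up only.
- Phase reading: follow-up opens on Day 21 and also takes the Day 29 laboratory result, so the follow-up window holds four laboratory results (Days 29, 34, 57, 85) instead of three.

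**What happens to the Day 85 result.** For laboratory, if the follow-up target is taken to mean the actual follow-up visit, the closest-record rule picks Day 34 and the Day 85 result goes unused. For SARA, Day 85 competes with the follow-up visit and no rule decides. In both cases Week 12 has no value.

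**Comparison within the SAP.** Week 12 is [78, EOS] for vital signs (Table 9) and [71, EOS] for ECG (Table 12). Those tables have no follow-up row, since Protocol Table 4 schedules neither measurement at that visit. Even so, one Day 85 visit by one early stopper counts as Week 12 for vital signs and ECG but not for laboratory or SARA.

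**The case against.** Five points can be made in the plan's defence.

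1. **Reach.** A reader might infer that Week 12 safety as a whole is misreported or that abnormal values are lost. The documents do not support that. Laboratory shift and markedly abnormal tables and the liver criteria use post-baseline values without these windows (SAP 4.5.3.2), and listings keep every laboratory and SARA result. SARA has no planned test. The efficacy windows (SAP Tables 2 to 4) use fixed days. This stands, and it limits the point to by-visit summaries.

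2. **The follow-up row.** A reader might infer that the laboratory follow-up row necessarily mixes values at two weeks and many weeks off drug. If the target means the actual visit, it does not, provided that visit took place. Mixing remains possible for SARA, or where the follow-up visit is missing.

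3. **Collection.** Protocol 10.1 sets a minimum for visits after stopping: adverse events, concomitant medication and key clinical assessments. Laboratory tests and SARA are not named in it, so not every retained subject need have a Day 85 result. This stands; the fault applies where a result exists.

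4. **Numbers.** It is tempting to use the 30% drop-out rate from the sample-size section. That figure is an allowance for drop-out in the power calculation. It does not measure the group that stops drug and keeps attending.

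5. **Intent.** Keeping off-drug values out of an on-drug Week 12 row is a defensible aim. The tables do not carry it out: in the example the off-drug Day 57 laboratory result still fits Week 8, and Tables 9 and 12 keep the off-drug Day 85 visit in Week 12.

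**Conclusion.** Tables 6 and 11 are wrong as written. This is more than missing detail, because a stated rule excludes results from the visit at which they were taken. For subjects who stop drug early but stay, a Day 85 laboratory or SARA result falls outside Week 12 for last doses through Day 71 if follow-up starts at its visit, or through Day 84 if it starts with the phase. On the visit reading, the Week 12 window is void for last doses through Day 57 (laboratory) and Day 50 (SARA). The cutoffs differ between readings, but the fault is present in both. Earlier scheduled results can fit two windows.

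The conclusion assumes nominal visit days (the working gives the shift for ±3 days) and that the assessment was done. The effect is confined to descriptive by-visit laboratory and SARA summaries. For SARA, that is the only planned summary other than listings. The number of subjects affected cannot be derived from the documents.

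**What to change.** In SAP Tables 6 and 11:

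- Fill the follow-up row from the nominal follow-up visit, 14 days after last dose.
- Map all other results by fixed day windows, with Week 12 as [71, end of study] for laboratory and [64, end of study] for SARA, in line with the vital-sign and ECG tables. A Day 85 result then stays in Week 12 for every last-dose day.
- When the follow-up visit coincides with a scheduled visit, use the result in both rows. With a last dose on Day 71 both visits fall on Day 85, and removing the follow-up result from the scheduled windows would empty Week 12 again.
- Give SARA the closest-record rule already used for laboratory data.
- Flag results taken after the last dose as off-treatment, so that Week 12 can also be shown for on-treatment results only.

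The cost is SAP wording and a small change to the visit-mapping program. No new data are needed.

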7.1. Study Duration for Subjects

The maximum total duration of study participation for each subject will be approximately 19 weeks including a screening phase of approximately 5 weeks, a treatment phase of approximately 12 weeks, and a safety follow-up phase of approximately 2 weeks.

The end of study date for a subject may be the last study visit, last follow-up telephone conversation, or last protocol-specified assessment. If the subject has ongoing AEs that are being followed, the end of study date may be the date of AE resolution.

7.2. Rater Qualifications

For specific rating assessments, only qualified raters will be allowed to evaluate and/or rate subjects in this study. The minimum qualifications a rater must meet for each study rating assessment will be outlined in the Study Reference Manual. It is recommended that, whenever possible, subjects and informants be interviewed and assessed throughout the study by the same rater. Reasons for changes in certified raters should be documented in the source. The Study Reference Manual provides a detailed description of specific study assessment information.

7.3. Study Stopping Rules

The Sponsor can terminate this study, after informing the Investigator, at any time. The Investigator will be notified by the Sponsor if the study is placed on hold, completed, or closed.

Stopping criteria for a seizure event are as follows:

- The study may be stopped if 1 subject experiences a seizure (postdosing and confirmed following unblinding to be on active study treatment), with a diagnosis of seizure confirmed by an independent panel of neurologists where no other cause has been identified. The process is described as follows:
 - If any subject has a suspected seizure event, individual dosing will be stopped immediately.
 - All available information regarding the seizure event including a Diagnostic Interview for Seizure Identification form will be provided to an independent panel of neurologists for review and adjudication as to the diagnosis and the possible relationship to the blinded study treatment.
 - The Sponsor will provide the outcome of the adjudication to the Independent Data Monitoring Committee (IDMC). If the IDMC recommends terminating the study, the Sponsor will unblind the treatment allocation for the subject who experienced the seizure. The study may be terminated by the Sponsor on recommendation of the IDMC.

CONFIDENTIAL

The information contained herein may not be used, disclosed, or published without the written consent of Biogen MA Inc.

The Sponsor and the IDMC will review safety data on an ongoing basis. The study may be modified or terminated based on recommendation of the IDMC or at the discretion of the Sponsor.

7.4. End of Study

The end of study is last subject, last visit.

CONFIDENTIAL

The information contained herein may not be used, disclosed, or published without the written consent of
Biogen MA Inc.

8. SELECTION OF SUBJECTS

8.1. Inclusion Criteria

To be eligible to participate in this study, candidates must meet the following eligibility criteria at the time of randomization, or at the timepoint specified in the individual eligibility criterion listed:

1. Evidence of a personally signed and dated informed consent document at the time of Screening indicating that the subject has been informed of all pertinent aspects of the study.
2. Evidence of a personally signed and dated informed consent for the informant indicating the informant has been informed of all pertinent aspects of the study. Informant consent must be signed prior to the in-person informant interview conducted during Screening.
3. Otherwise healthy male and/or female subjects from age 18 to 55 years, inclusive, with a Diagnostic and Statistical Manual of Mental Disorders, Fifth Edition (DSM-5), diagnosis of schizophrenia of at least 2 years duration as confirmed by the MINI 7.0.2 for Psychotic Disorders. The MINI 7.0.2 for Psychotic Disorders will also be used to exclude comorbid diagnoses. In addition, diagnosis of schizophrenia must be deemed “valid” by remote, independent raters using prespecified criteria (see Section 9.1.1.3).
4. Evidence of stable schizophrenia symptomatology ≥ 12 weeks (e.g., no hospitalizations for schizophrenia, no increase in level of psychiatric care due to worsening of schizophrenia symptoms).
5. Subjects must be receiving ongoing maintenance atypical antipsychotic therapy (except clozapine), on a stable treatment regimen for ≥ 8 weeks prior to Baseline/Day 1, including concomitant psychiatric medications. Doses of background atypical antipsychotics should be within the recommended dose range listed in the approved product labeling of the country where the study is being conducted. Doses exceeding the recommended dose range are not permitted and doses below the recommended dose range should be discussed with the Sponsor's Medical Monitor (see Section 11.4.1).
 - Treatment regimen stability is defined as maintaining the same dosage of treatments except for minor adjustments ($\leq 25\%$) to manage medication-specific tolerability issues. Recognizing that physicians outside of the study may be managing the subject's background antipsychotic and other psychiatric medications, changes in background antipsychotic and psychiatric medications should be discussed with the Sponsor's Medical Monitor.
 - Stable concomitant treatment with a second atypical antipsychotic, at doses that do not exceed the range listed in the approved product labeling of the country where the study is being conducted, is permissible if used for a targeted symptom

CONFIDENTIAL

The information contained herein may not be used, disclosed, or published without the written consent of
Biogen MA Inc.

(e.g., insomnia) or an adverse effect from the primary maintenance antipsychotic treatment, but not if it is used for refractory psychotic symptoms. Treatment regimen stability as defined above applies to the second antipsychotic. **Subjects should be taking no more than 2 background antipsychotics.**

- Note that hypnotics are an exception to the treatment regimen stability requirement; prohibited hypnotics may be substituted with allowed hypnotics administered as described in Section [11.4.1](#).
- 6. Must be willing and able to comply with scheduled visits, treatment plan, laboratory tests, and other study procedures.
- 7. Must have an identified informant (e.g., family member, social worker, caseworker, or nurse who interacts [in person or by telephone] with the subject at least 2 times per week) who should, whenever possible, be consistent throughout the study and considered reliable by the Investigator.
- 8. Must reside in a stable living situation, in the opinion of the Investigator, for at least 12 weeks prior to Screening and be expected to remain in a stable living situation for the duration of the study.
- 9. Must have oral fluency in the test language confirmed by a standard score of ≥ 70 at Screening on a validated reading assessment test (please refer to the Study Reference Manual for appropriate reading test). Non-native speakers of the test language must have at least 7 years of formal education in this language.
- 10. All women of childbearing potential and all men must practice highly effective contraception during the study and for at least 30 days after the last dose of study treatment. For further details of contraceptive requirements for this study, refer to Section [15.5](#).
- 11. Body mass index of 17.5 to 45.0 kg/m² and total body weight >50 kg (110 lb). Subjects with a BMI >40.5 kg/m² must be discussed with the Sponsor's Medical Monitor to determine subject eligibility.
- 12. SCI-PANSS: No more than moderate-severe rating (score ≤ 5) on delusions, hallucinatory behavior, grandiosity, suspiciousness/persecution, and hostility (i.e., PANSS, positive symptom items P1, P3, P5, P6, P7), or unusual thought content (G9); and no more than a moderate rating (score ≤ 4) on conceptual disorganization (P2).
- 13. At least 80% dosing regimen compliance during the Placebo Lead-In period.

CONFIDENTIAL

The information contained herein may not be used, disclosed, or published without the written consent of Biogen MA Inc.

